5.5.3.2 Assessment of Extramedullary Plasmacytoma

CT or MRI should be performed in all subjects if clinically indicated at baseline to assess for the presence of extramedullary plasmacytoma. To minimize unnecessary radiation in myeloma subjects where progression is primarily based on serum and urine M-protein, on study assessments should only be performed if clinically indicated (ie, pain, concern for disease progression), whether or not present at baseline, and at the time of CR/sCR assessment.

A sum of the products of the longest diameters and longest perpendicular diameter for all measurable lesions will be calculated at baseline. This sum will be used as the reference for on study assessments by which to characterize the objective tumor response.

All tumor measurements must be made in millimeters. All documented measurable lesions are to be followed throughout the trial. All assessments to be used for tumor response evaluation, including the baseline assessment, must be performed using the same method for repeat assessment. CT and MRI scanning are the preferable methods of assessment. Conventional CT and MRI should be performed with contiguous cuts of 10 mm or less or with cuts of 5 (or 10) mm if spiral CT scanning is used. Imaging-based evaluation is preferred to evaluation by clinical examination. Evaluation by chest x-ray is less preferable than CT or MRI, and should only be used for well-defined lesions surrounded by aerated lung. Clinical examination is only acceptable when lesions are superficial, such as a skin nodule or palpable lymph node. Skin lesions must be documented by a photograph with a ruler. Ultrasound is not acceptable for documentation of measurable disease.

Duplicate copies of all imaging studies used for tumor response evaluation will be made available for review by the Sponsor upon request.

Measurable disease are lesions that can be accurately measured in 2 dimensions and both diameters must be ≥ 20 mm when evaluated by standard CT scanning or ≥ 10 mm when evaluated by spiral CT scanning. The minimum diameter size should be at least twice the slice thickness.

Non-measurable disease are all other lesions (or sites of disease), including those that are too small (ie, do not meet above criteria), occur within a previously irradiated area (unless they are documented as new lesions since the completion of radiation therapy), bone lesions, leptomeningeal disease, ascites, pleural or pericardial effusion (exception for effusions documented by cytology as not malignant or present at baseline without progression), lymphangitis cutis/pulmonis, abdominal masses that are not pathologically/cytologically confirmed and followed by imaging techniques, and cystic lesions.

5.5.4 Definitions of Response Based on IMWG

See Table 5.5.4-1 and Table 5.5.4-2 for definitions of response and progression. All criteria are derived from IMWG.²¹ All response categories require 2 consecutive assessments. The second of the 2 consecutive assessments should occur at the next planned tumor assessment (every 4 weeks after the first dose).

Table 5.5.4-1: IMWG Criteria for Response

Category	Criteria ^a
Stringent Complete response (sCR)	CR as defined below plus Normal serum free light chain (FLC) ratio and Absence of clonal cells in bone marrow ^b by immunohistochemistry or immunofluorescence. ^c
Complete response (CR)	The first two bullet points must be met. The remaining bullet points must be met only as indicated. Negative immunofixation on both serum and urine and, Bone marrow aspirate ^b containing < 5% plasma cells, No increase in size or number of lytic lesions should occur (development of a compression fracture does not exclude response) with disappearance of soft tissue plasmacytomas, Skeletal survey must be performed ONLY if clinically indicated.
Very Good partial Response (VGPR)	Serum and urine M-protein detectable by immunofixation but not on electrophoresis or 90% or greater reduction in serum M-protein plus urine M-protein < 100 mg per 24h. If the serum and urine M-protein are unmeasurable, a ≥ 90% decrease in the difference between involved and uninvolved FLC levels is required in place of M-protein criteria.
Partial response (PR)	All of the following conditions must be met for PR: Greater than or equal to 50% reduction in serum M-protein and Reduction of ≥ 90% in urinary M-protein or a decrease to < 200 mg/24 hours, If the serum and urine M-protein are unmeasurable, a ≥ 50% decrease in the difference between involved and uninvolved FLC levels is required in place of M-protein criteria. Greater than or equal to 50% reduction in the size of soft tissue plasmacytomas present at baseline, No increase in size or number of lytic bone lesions (development of a compression fracture does not exclude response). Skeletal survey must be performed ONLY if clinically indicated to confirm that lytic lesions have not increased and that no new lesions are seen; if done, this should occur at the 4-week confirmatory time point following initial determination of PR.

Table 5.5.4-1: IMWG Criteria for Response

Category	Criteria ^a
Stable disease (SD)	Not meeting criteria for CR, VGPR, PR or progressive disease.

^a All response categories require two consecutive assessments made at anytime; all categories also require no known evidence of progressive or new bone lesions if radiographic studies were performed. Radiographic studies are not required to satisfy these response requirements.

^b Confirmation with repeat bone marrow biopsy not needed.

^c Presence/absence of clonal cells is based upon the κ/λ ratio. An abnormal κ/λ ratio by immunohistochemistry and/or immunofluorescence requires a minimum of 100 plasma cells for analysis. An abnormal ratio reflecting presence of an abnormal clone is κ/λ of $> 4:1$ or $< 1:2$.

Table 5.5.4-2: IMWG Criteria for Progression

Category	Criteria ^a
Progression of Disease (PD)	
Progression describes a definite increase in disease activity relative to the nadir in subjects. One or more of the following constitutes PD:
 
 Increase of $\geq 25\%$ in serum monoclonal paraprotein (must also be an absolute increase of at least 5 g/L)^b and confirmed by at least one investigation, Increase of $\geq 25\%$ urinary light chain excretion (which must also be an absolute increase of at least 200 mg/24-hours) and confirmed by at least one investigation, Only in subjects without measureable serum and urine M-protein levels: the difference between involved and uninvolved FLC levels must increase by $\geq 25\%$ and confirmed by at least one investigation. The absolute increase must be > 10 mg/dL. Increase of $\geq 25\%$ plasma cell percentage in the marrow (which must also be an absolute increase of at least 10%) Definite increase in the size of lytic bone lesions or soft tissue plasmacytomas, Development of new bone lesions or soft tissue plasmacytomas or definite increase in the size of residual bone lesions (development of a compression fracture does not exclude continued response and may not indicate progression), Development of hypercalcemia (corrected serum calcium greater than 11.5 mg/dL; 2.65 mmol/L) not attributable to any other cause.

^a All categories require two consecutive assessments made at any time before classification as disease progression and/or the institution of any new therapy.

^b For progressive disease, serum M-component increase of ≥ 1 g/dl is sufficient to define progression if starting M-component is ≥ 5 g/dL.

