3.3.1 Inclusion Criteria

1. Signed Written Informed Consent

- a) Subject is, in the investigator's opinion, willing and able to comply with the protocol requirements.
- b) Subject has given voluntary written informed consent before performance of any study related procedure not part of normal medical care, with the understanding that consent may be withdrawn by the subject at any time without prejudice to their future medical care.

2. Target Population

- a) Eastern Cooperative Oncology Group (ECOG) performance status ≤ 2 .
- b) Life-expectancy > 3 months.
- c) Newly diagnosed, untreated, symptomatic, documented myeloma AND;
 - i) Who are not candidates for high-dose therapy plus SCT because of age (≥ 65 years) or coexisting conditions. Refusal to undergo high dose therapy with SCT is **NOT** sufficient for entry onto CA204116 for a subject < 65 years old. There must be a comorbidity that prevents SCT for a subject < 65 years old, AND;
 - ii) Measureable disease (patient must meet one of these criteria)
 - (a) serum IgG M-protein ≥ 0.5 g/dL OR
 - (b) serum IgA M-protein ≥ 0.5 g/dL OR
 - (c) serum IgM M-protein ≥ 0.5 g/dL OR
 - (d) Urine M-protein ≥ 200 mg/24-hour OR
 - (e) Serum free light chain (sFLC) assay showing involved FLC level ≥ 10 mg/dL (≥ 100 mg/l) provided the serum FLC ratio is abnormal
- d) Subject Re-enrollment: This study does not permit the re-enrollment of a subject that has discontinued the study as a pre-treatment failure.

3. Age and Reproductive Status

- a) Males and Females, ages ≥ 20 years, inclusive
- b) Subjects must be willing to refrain from blood donations during study drug therapy and for 90 days after therapy.
- c) Women of childbearing potential (WOCBP) and men must be using 2 acceptable methods of contraception to avoid pregnancy throughout the study for a period of at least 1 month (4 weeks) before study treatment and women for up to 120 days, men for up to 180 days after the last dose of study drug in such a manner that the risk of pregnancy is minimized. See [Section 3.3.3](#) for the definition of WOCBP and also refer to the Revlimid risk management plan guidelines.

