- e) Plasma cell leukemia (defined as either $\geq 20\%$ of peripheral WBC comprised of plasma/CD138⁺ cells or an absolute count of $\geq 2 \times 10^9/L$).

2. Medical History and Concurrent Diseases

- a) POEMS syndrome (plasma cell dyscrasia with polyneuropathy, organomegaly, endocrinopathy, monoclonal protein, and skin changes).
- b) Significant cardiac disease as determined by the investigator including:
 - i) Known or suspected cardiac amyloidosis;
 - ii) Congestive heart failure of Class III or IV of the NYHA classification;
 - iii) Uncontrolled angina, hypertension or arrhythmia;
 - iv) Myocardial infarction in past 6 months;
 - v) Any uncontrolled or severe cardiovascular disease.
- c) Prior cerebrovascular event with persistent neurologic deficit.
- d) Known HIV infection or active hepatitis A, B, or C.
- e) Any medical conditions that, in the investigator's opinion, would impose excessive risk to the subject. Examples of such conditions include:
 - i) Any uncontrolled disease, such as pulmonary disease, infection, seizure disorder;
 - ii) Active infection that requires parenteral anti-infective treatment;
 - iii) Any altered mental status or any psychiatric condition that would interfere with the understanding of the informed consent.

- f) Prior or concurrent malignancy, except for the following:
 - i) Adequately treated basal cell or squamous cell skin cancer;
 - ii) Or any other cancer from which the subject has been disease-free for > 5 years.
- g) Unable to tolerate thromboembolic prophylaxis including, aspirin, Coumadin (warfarin) or low-molecular weight heparin as clinically indicated.

3. Physical and Laboratory Test Findings

- a) Corrected serum calcium \geq 11.5 mg/dl within 2 weeks of randomization (despite appropriate measure such a short course of steroids, bisphosphonates, hydration, calcitonin).
- b) Absolute neutrophil count $<$ 1000 cells/mm³. No granulocyte colony stimulating factors (G-CSF or GM-CSF) allowed within 1 week of randomization. No pegylated granulocyte colony stimulating factors allowed within 3 weeks of randomization.
- c) Platelets $<$ 75,000 cell/mm³ (75 x 10⁹/L). Qualifying laboratory value must occur at most recent measurement prior to randomization and must be no more than 14 days prior to randomization. No transfusions are allowed within 72 hours prior to qualifying laboratory value.

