3.5 Discontinuation of Subjects followings any Treatment with Study Drug

Subjects MUST discontinue investigational product (and non-investigational product at the discretion of the investigator) for any of the following reasons:

- Subject's request to stop study treatment
- Any clinical adverse event (AE), laboratory abnormality or intercurrent illness which, in the opinion of the investigator, indicates that continued participation in the study is not in the best interest of the subject
- Pregnancy (Subject must discontinue elotuzumab and lenalidomide).
- Termination of the study by Bristol-Myers Squibb (BMS)
- Loss of ability to freely provide consent through imprisonment or involuntarily incarceration for treatment of either a psychiatric or physical (eg, infectious disease) illness
- Progressive Disease (see [Section 5.5.4](#) for definition of disease progression).
- Subjects who receive any non-protocol specified systemic anti-myeloma therapy prior to documented progression will be discontinued from all study treatment (including lenalidomide/dexamethasone), however, tumor assessments must continue at 4 week intervals until documented progression.
- Subjects experiencing a Grade 4 infusion reaction must discontinue elotuzumab. Subjects may continue lenalidomide and dexamethasone treatment. Refer to [Section 4.5.2.2](#).

- Subjects experiencing angioedema, Grade 4 rash, exfoliative or bullous rash, Stevens Johnson syndrome, or toxic epidermal necrolysis related to lenalidomide must discontinue lenalidomide. Subjects in the elotuzumab arm may continue elotuzumab and dexamethasone.
- Subjects experiencing a 28-day delay in all study drugs lenalidomide, dexamethasone, and elotuzumab due to an adverse event(s) related to study treatment must be discontinued from study drug. Subjects experiencing delays unrelated to study therapy, for example due to radiation therapy may delay study treatment up to 42 days. Delays greater than 28 days must be discussed with the medical monitor.

In the case of pregnancy, the investigator must immediately notify the BMS Medical Monitor/designee of this event. In most cases, the study drug will be permanently discontinued in an appropriate manner. If the investigator determines a possible favorable benefit/risk ratio that warrants continuation of study drug, a discussion between the investigator and the BMS Medical Monitor/designee must occur.

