5.5 Efficacy Assessments

Efficacy endpoints will be based on serum and urine protein electrophoresis (SPEP and UPEP), corrected calcium (serum calcium and serum albumin), and bone marrow assessments at predefined intervals as specified in [Table 5.1-1](#), [Table 5.1-2](#), and [Table 5.1-3](#). Assessments for SPEP and UPEP will be based on central lab results, whereas assessments of bone marrow, bone lesions, extramedullary plasmacytomas, and corrected calcium will be based on local analysis at the site. Serum β 2 microglobulin will be performed locally at screening. If SPEP and UPEP M protein are performed at a local laboratory, results must be recorded in the CRF/eCRF.

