4) **Serum corrected calcium:** Serum corrected calcium should be collected with each cycle for all subjects until disease progression.

5.5.3 **Imaging Assessments for Myeloma**

5.5.3.1 **Skeletal Survey**

Skeletal survey, by conventional radiography, for metastatic disease will be performed at screening (within 28 days prior of randomization), and on study if clinically indicated (development of compression fracture does not exclude response). Use of conventional or low dose CT scan (ie, of the spine) or MRI bone survey is acceptable. If imaging is performed on treatment for assessment of progression, the site must use the same modality of imaging as used in screening. The number and location of skeletal lesions and whether they are lytic should be

recorded on the eCRF. On treatment survey should record whether there is an increase in the number or size of lytic lesions.

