4.1.3 Duration of Response

Duration of response will be measured for subjects whose best response is PR or better, from the time that the criteria for objective response are first met until the date of a progression event (according to the primary definition of PFS). A subject with objective response who does not have a progression event will be censored at the same time they were censored under the primary definition of PFS.

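### The hypercalcaemia criterion for progression prints two unequal thresholds as one: 11.5 mg/dL is 2.87 mmol/L, while 2.65 mmol/L is 10.6 mg/dL

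*Protocol*

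**What the plan says.** Protocol section 5.5.4, Table 5.5.4-2, lists the findings that define progressive disease, any one of which is enough. The last is hypercalcaemia with no other cause, defined as "corrected serum calcium greater than 11.5 mg/dL; 2.65 mmol/L". Footnote a adds a confirmation rule: "All categories require two consecutive assessments made at any time before classification as disease progression".

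The only other calcium cut-off is in section 3.3.2, exclusion criterion 3(a), which bars subjects at or above "11.5 mg/dl within 2 weeks of randomization". It is given in mg/dL alone. The SAP states no calcium threshold.

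The criterion is in routine use:

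- Section 5.5.2, item 4: "Serum corrected calcium should be collected with each cycle for all subjects until disease progression".
- Section 5.5: "corrected calcium will be based on local analysis at the site".
- Section 3.1: the investigator assesses progression, and no independent review is planned.
- Section 3.5: progressive disease is among the reasons for which "Subjects MUST discontinue investigational product".
- SAP section 7.1: PFS uses the progression date that the investigator assigns.
- SAP section 4.1.3: duration of response runs "until the date of a progression event (according to the primary definition of PFS").

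**The concern.** Two numbers with different units inside one parenthesis, separated by a semicolon, can only be read as the same limit expressed twice. They are not the same limit. The protocol's other dual-unit limit for a myeloma marker, the free light chain entry criterion in section 3.3.1 ("assay showing involved FLC level ≥ 10 mg/dL (≥ 100 mg/l"), does convert correctly.

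An investigator working in mg/dL and one working in mmol/L could therefore both follow the table and reach opposite conclusions on the same patient. At stake are whether and when progression is recorded, whether treatment must stop, and the PFS and duration-of-response times that follow. With no planned independent review, no later step would bring the two readings into line.

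**Working it through.** **Inputs.** The printed pair, 11.5 mg/dL and 2.65 mmol/L, comes from Protocol Table 5.5.4-2. The arm size of 40 comes from Protocol section 8.1. The molar mass of calcium, 40.08 g/mol, is a physical constant that the documents do not give; 40.0 to 40.1 was used as a range.

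**Attempt to reproduce the printed SI figure.** mmol/L = (mg/dL × 10) / molar mass.

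- 11.5 × 10 / 40.08 = 2.87 mmol/L, not 2.65.
- Over the range of molar mass: 115 / 40.0 = 2.875 and 115 / 40.1 = 2.868.
- With the rounded factor 0.25: 11.5 × 0.25 = 2.875. With 0.2495: 2.869.
- In mEq/L (twice the mmol/L value): 5.74.
- Molar mass at which the pair would agree: 115 / 2.65 = 43.4 g/mol, which is not that of calcium.

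No variant gives 2.65.

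**Reverse conversion.** mg/dL = mmol/L × molar mass / 10.

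- 2.65 × 40.08 / 10 = 10.62 mg/dL (10.60 to 10.63 over the range).

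**Gap.**

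- 11.5 − 10.62 = 0.88 mg/dL, and 0.88 / 11.5 = 7.6%.
- 2.87 − 2.65 = 0.22 mmol/L.

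**How the two figures classify the same patient.** Assume the rise is new, confirmed on two consecutive assessments and has no other cause, and that no other progression criterion is met.

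| Corrected calcium | By 11.5 mg/dL | By 2.65 mmol/L |
|---|---|---|
| Up to 10.6 mg/dL | Not PD | Not PD |
| Above 10.6, up to 11.5 mg/dL | Not PD | PD |
| Above 11.5 mg/dL | PD | PD |

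**Comparison with eligibility.** Exclusion 3(a) admits subjects with corrected calcium just under 11.5 mg/dL. The SI cut-off of about 10.6 mg/dL lies inside that eligible range, so a subject could enter already above the SI limit for progression. This favours 11.5 mg/dL as the intended limit but does not prove it.

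**Effect of one reclassified subject.** 1 / 40 = 2.5 percentage points of an arm's PFS rate at 1 or 2 years. This applies if that subject would otherwise have been progression-free at that time and no one was censored earlier; with earlier censoring the shift is larger.

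**The case against.** The strongest reply accepts the arithmetic and disputes the weight. For the error to matter, a subject's calcium must newly rise into a band 0.88 mg/dL wide, stay there on two consecutive assessments, have no other explanation and occur without any other progression criterion. The investigator must also apply the SI figure. The trial runs in one country, the mg/dL value is printed first, and the eligibility limit is in mg/dL only. A site working in mg/dL would read 11.5 in both places, and nothing shows that any site reports calcium in mmol/L. PFS is a secondary endpoint, no formal comparison between arms is planned (SAP section 5), the same table applies to both arms, and no direction of bias is evident. The 2.5-point figure would hold for any single misclassified subject and says nothing about how likely one is.

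All of this stands as a limit on size, but it does not say which number governs. The free light chain comparison is also weak evidence, because that conversion is only a decimal shift.

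A further point is that section 5.5.4 says the criteria derive from the IMWG. That source was not available, so it is not known whether the pair was carried over from it. If it was, this protocol would still give its sites two different limits. The clinical team should nevertheless check the source before choosing which figure to keep.

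**Conclusion.** The concern holds. The criterion is wrong as printed: its two values cannot both be the threshold, and neither document resolves the conflict. The conclusion rests only on the molar mass of calcium and is the same over any plausible rounding.

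The practical effect is probably small. It is confined to corrected calcium above 10.6 and up to 11.5 mg/dL (above 2.65 and up to 2.87 mmol/L) under the conditions set out above. The number of subjects affected, and whether any site uses mmol/L, cannot be determined from the documents. PFS, duration of response and the decision to stop treatment are exposed. The sample size and the 32-of-40 decision rule are not, and an effect on the primary response rate is unlikely. It should be corrected because it leaves an endpoint event and a mandatory stopping rule open to two readings.

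**What to change.** State one limit in Table 5.5.4-2. The default is to keep 11.5 mg/dL, which agrees with exclusion 3(a), and to change the SI value to 2.87 mmol/L. If the clinical team, after checking the cited response criteria, confirms that 2.65 mmol/L was intended, change the mg/dL value to 10.6 instead. Tell sites which limit governs, and check any progression already called on calcium alone against it, so that one definition holds throughout.

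The cost is a one-line clarification and a site notice. Under Protocol section 9.1.1, an amendment needs IRB approval, and an administrative letter requires that the IRB be informed. No analysis method or sample size changes.

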5.6 Pharmacokinetic Assessments

Blood samples for PK assessment will be drawn according to the PK sampling schedule given in Table 5.6-1. PK samples will be collected according to the schedule listed in Table 5.6-1 in all subjects received elotuzumab. Blood samples for the analysis of serum concentrations of elotuzumab should be drawn from the arm not used for infusion of study drug.

In addition, Development of anti-drug antibodies (ADA) to elotuzumab will be evaluated in all subjects received elotuzumab at specified time points as noted in Table 5.6-1.

Table 5.6-1: PK and ADA Sampling Schedule

Cycle Number	Study Day	Time (Event) ^a	PK	ADA
1	1	0 H (pre-dose)	X	X
		2 hours post-end of infusion	X	
	8	0 H (pre-dose)	X	
		2 hours post-end of infusion	X	
	15	0 H (pre-dose)	X	
		2 hours post-end of infusion	X	
22	0 H (pre-dose)	X		
	2 hours post-end of infusion	X		
2	1	0 H (pre-dose)	X	X
		2 hours post-end of infusion	X	
	22	0 H (pre-dose)	X	
		2 hours post-end of infusion	X	
3	1	0 H (pre-dose)	X	X
		2 hours post-end of infusion	X	
	8	168 hours	X	
		15	0 H (pre-dose)	X
4	1	0 H (pre-dose)	X	
6	1	0 H (pre-dose)	X	X
9	1	0 H (pre-dose)	X	X
12	1	0 H (pre-dose)	X	X
15	1	0 H (pre-dose)	X	X
18	1	0 H (pre-dose)	X	X
Every 3 cycles thereafter (eg, Cycle 21, 24, 27, etc.)	1	0 H (pre-dose)	X	X

Table 5.6-1: PK and ADA Sampling Schedule

Cycle Number	Study Day	Time (Event) ^a	PK	ADA
	End of Study / Discontinuation ^b		X	X
	30-Day Follow-up ^b		X	X
	60-Day Follow-up ^b		X	X

^a For subjects who miss a dose(s) of elotuzumab, collect PK and ADA samples on the planned day, or if the sampling is unavailable, collect samples on the day (predose) that elotuzumab is restarted (noting the actual time of collection and dosing), and then continue following the schedule in [Table 5.6-1](#).

^b For subjects who discontinue elotuzumab only, but otherwise continue on study treatment, collect PK and ADA samples at the day of elotuzumab discontinuation, 30 and 60 days after the last elotuzumab dose.

[REDACTED]

[REDACTED]	[REDACTED]	[REDACTED]	[REDACTED]
[REDACTED]	[REDACTED]	[REDACTED]	[REDACTED]
[REDACTED]	[REDACTED]	[REDACTED]	[REDACTED]
[REDACTED]	[REDACTED]	[REDACTED]	[REDACTED]
[REDACTED]	[REDACTED]	[REDACTED]	[REDACTED]

[REDACTED]

